9.1 Data Monitoring

The purpose of monitoring visits is to confirm that studies sponsored by Laboratorios Sophia , SA de CV are conducted in accordance with the ethical principles established in the Declaration of Helsinki, with Good Clinical Practices, and with applicable regulatory requirements. The site monitor must verify compliance with the protocol, amendment(s), review accounting records for the investigational product, and verify that the site personnel and facilities are adequate for conducting the study.

The researcher must ensure that sufficient time, space, and qualified personnel are available for monitoring visits.

In order to conduct the monitoring review, it is mandatory to provide direct access to all source data and data related to the study site. The monitor will conduct a review of the CRF and a Source Document Verification (SDV). SDV refers to the verification of records in the CRF by comparing them with the source data that the researcher will make available for this purpose.

Regarding the CRF, the monitor will mark the completed and approved screens on each visit if the electronic platform is used.

In accordance with applicable regulations, Good Clinical Practices, and the procedures of Laboratorios Sophia , SA de CV, Laboratorios Sophia , SA de CV monitors will contact the site prior to the start of the study to review the protocol, regulatory, ethical, and Laboratorios Sophia , SA de CV requirements with site personnel. When reviewing procedures for data collection, the discussion will also include the identification, agreement, and documentation of individual data for which the records in the CRF will serve as source documents.

Laboratorios Sophia , SA de CV will monitor the study to verify, among other things, that:

- The data is authentic, correct and complete.
- The safety and rights of the subjects are being protected.
- The study is being conducted in accordance with the currently approved protocol, any other study agreements, Good Clinical Practices, and all applicable regulatory requirements.

The investigator and the head of the medical institution (when applicable) agree to allow the monitor direct access to all relevant documents.

Study monitoring visits will be conducted at regular intervals, depending on the recruitment rate, under arrangements between the investigator and the sponsor. All information related to these visits will be treated as strictly confidential.

Upon premature completion or discontinuation of the study, the monitor will conduct site closure activities with the investigator or site personnel, as appropriate, in accordance with applicable regulations, Good Clinical Practices, and Laboratorios Sophia , SA de CV procedures.

After the study is closed, the investigator must maintain all study records on-site in a secure location. Records must be maintained to allow for easy and timely retrieval, when necessary (e.g., during an audit or inspection). Laboratorios Sophia , SA de CV will inform the investigator/institution of the length of time these records must be retained in order to comply with all applicable regulatory requirements. However, the investigator/institution must seek written approval from the sponsor before disposing of these records. The minimum retention period will satisfy the most stringent standard applicable to that study site, as set forth in GCP, any institutional requirements, or applicable laws or regulations, or the standards/procedures of Laboratorios Sophia , SA de CV.

The researcher/institution must notify Laboratorios Sophia , SA de CV of any changes in archiving arrangements including, but not limited to, the following: archiving in an off-site facility, transfer of ownership of records in the event the researcher leaves the site.

9.2 Preliminary analysis and early termination of the study

If a partial analysis is required, as described in section 8.3.2, this will allow the sponsor to make a decision about early termination of the study if the safety of the participants is compromised.

Early termination of the study will be considered in the following cases:

1. Presence of serious adverse events in more than 5% of participants in any intervention group.
2. The competent authority (COFEPRIS) considers it as security alerts.
3. The Sponsor determines this for its convenience or eventualities such as: financial support, manufacturing errors, etc.
4. Lower recruitment than expected.

If the decision is to terminate the clinical study early, the research center will be notified within the first 24 hours, using the available means of communication. The corresponding authority and the Ethics Committees involved will also be informed.

The research center is required to inform subjects participating in the clinical study within 24 hours of receiving the information from the sponsor. All subjects involved in any phase of the study must be informed.

The outcome of the preliminary evaluation will be the responsibility of the Clinical Operations Management and the Medical Directorate of Laboratorios Sophia , SA de CV, which will have the authority to determine the fate of this protocol, as they deem appropriate.

9.3 Adverse events

9.3.1 Researcher Responsibilities

Conduct adverse event verification through questioning, a relevant physical examination, assessment of progress, as well as appropriate medical and pharmacological management, resolution or outcome, and final discharge following the definitions established in national and international regulations.[54] [55] [56]

In the event of adverse events or any occurrence that puts the health and well-being of patients at risk, appropriate medical care will be provided, either at the research site or by referring the patient to the Hospital Center with the highest resolution capacity with which the researcher's site and/or the researcher has a medical care agreement. The researcher will notify the sponsor's clinical monitor, in accordance with the times established in national and international regulations. In the case of serious adverse events, the sponsor will be notified and the corresponding information will be recorded in the case report form, and in turn, the Research Ethics Committee and the Research Committee will be informed.

The care of adverse events will be carried out according to the event care diagram (see **Figure 4Adverse event care**)

The final report to be drafted by the Scientific Committee of the Clinical Operations Department of Laboratorios Sophia , SA de CV, will include a report on adverse events in compliance with current national and international regulations. [55] [54]

9.3.1.1 Recording adverse events on the Case Report Form

The adverse event registry considers information concerning the participating patient's identification data such as code, age, sex, left eye, right eye.

Information about the type of adverse event, adverse reaction, or suspected adverse reaction to the investigational product or study drug, as applicable. The date on which the adverse event occurred is reported, as well as the date on which the Investigator became aware of it, and the date of resolution or outcome, as applicable. The clinical diagnosis is indicated. Include among concomitant medications the therapy used for the pharmacological management of the adverse

event, suspected adverse reaction, or adverse reaction. Record the outcome or resolution of the event: patient recovered without sequelae, with sequelae, or not recovered. Patient who died due to the adverse reaction/adverse event; patient who died and it is judged that the drug may have contributed; patient who died and the death was not related to the investigational product or drug; or indicate that the consequence of the event is unknown.

Record information about the investigational product or drug, or the drug associated with the adverse event, adverse reaction, or suspected adverse reaction. As applicable, information concerning the generic name, distinctive name, or code of the investigational product and/or investigational drug must be recorded, as appropriate according to the methodological design of the study. This is relevant in the case of blinded studies or those where placebo is used as a comparator, since there are circumstances that justify opening the blind to determine whether the adverse event, adverse reaction, or suspected adverse reaction may be attributable to the active agent, combination of active agents, or pharmacologically inert substance(s), such as vehicles or additives, as appropriate to the phase of clinical research in which the development of the drug is located. It will also be necessary to record data concerning the batch number, manufacturing laboratory, expiration date, dose, route of administration, start and end dates of administration and/or consumption, reason for the prescription; depending on whether it is a product or medication under investigation (protocol in which the patient is currently participating) or a medication that the subject under investigation consumes for the treatment of concomitant underlying diseases or uses for the management of some temporary sign or symptom that does not correspond to the Natural History of the pathology that motivated his/her entry into the research protocol.

Record the withdrawal or discontinuation of the drug, investigational product, or investigational drug, as appropriate. Indicate whether the adverse event disappears upon withdrawal of the investigational product, investigational drug, or suspected drug (of causing the event). Also indicate whether a dose adjustment is made, if the event changes in intensity or severity, and if the reaction persists. It is important to note that in patients who are re-exposed to the investigational product, investigational drug, or drug, which had previously been discontinued, if the adverse reaction or event reappears .

Regarding concomitant pharmacotherapy, indicate the generic name, dose, route of administration, start and end dates, and the reason for the prescription, regardless of whether it is in accordance with the prescribing information or the data sheet or if it is used outside the regulations or as authorized by the local, national, or international regulatory body.

Regarding relevant clinical history. The analysis of the adverse event, adverse reaction, or suspected adverse reaction takes into account the previously described information. However, the clinical context in which the adverse event occurs in the participants of the clinical research protocol is of special interest. Therefore, information about previous conditions, hypersensitivity or allergy symptoms, previous surgical procedures, laboratory tests or examinations performed on the participant, etc., that the researcher deems appropriate may be mentioned. If there is not enough space in the case report form, the information from the clinical note may be supplemented in the clinical record.

9.3.1.2 Monitoring of adverse events

The PI will provide care and management of the participant's AE until its resolution, as described in the following section. If the participant develops a chronic adverse event during the study, the patient will only be monitored for 30 days after the last pharmacological intervention.

9.3.1.3 Procedures for a serious adverse event

The adverse event handling process considers the following stages:

[figure not shown]

Figure 4 Adverse event care

- A. During the development and conduct of this clinical research, undesirable harmful events or adverse reactions of medical significance may occur in the participating patient, which do not necessarily have a causal relationship with the investigational product or investigational drug. These harmful phenomena may occur during the use of investigational drugs, unintentionally, at doses authorized for use in humans by a local, national, or international regulatory entity, whether for prophylaxis, diagnosis, treatment, or for the modification of a physiological process. However, it may be suspected that the investigational product, the investigational drug, or the placebo may cause some unwanted clinical manifestation. Adverse events, adverse reactions, or suspected adverse reactions to one or more drugs may occur during the systematic evaluation of participants (on the days in which the clinical review is scheduled, according to the schedule of activities) or suddenly, in such a way that,
- B. The researcher must be the first person to whom the patient notifies that he or she has developed or experienced any harmful clinical phenomenon during his or her participation in this research protocol.
- C. In accordance with his or her clinical judgment; based on the pertinent physical examination, questioning, etc., as well as the analysis of the information available in the medical literature and that referred to in the investigator's manual, Prescribing Information or the comparator drug's data sheet, the principal investigator determines the appropriate treatment for the adverse event/reaction; whether
- D. at the research site or at the hospital with the highest resolution power (1st, 2nd or 3rd level of medical care). So that, in case the patient is referred by the Researcher to a hospital, he/she attends through a referral system, it may be with an identification card that the patient belongs to the present investigation and there is an office or folio number, which belongs to the emergency care agreement with the health institution with the highest resolution power or a medical reference note issued by the principal investigator is given to the participating patient so that appropriate care is provided. It should be noted that the

Sponsor of the study, Laboratorios Sophia , SA de CV, will pay the expenses for the medical care of the participating patient, only if the adverse event, adverse reaction or suspected adverse reaction to a medication is associated or related to the investigational product or investigational medication.

- E. Taking the clinical information collected, either during the care provided at the research site or that provided by the treating physician(s) at the hospital, the principal investigator records the adverse event, suspected adverse reaction or adverse reaction to medication in his/her clinical note in the clinical record, recording the seriousness, intensity (mild, moderate or severe), relationship with the product or medication under investigation, as well as:
- F. The migration of relevant data to the case report format and its respective adverse event section, indicating the pertinent information, already referred to in section 9.3.1.1. This is because in cases of serious adverse events, which must be reported within 24 hours after the principal investigator becomes aware of them, the clinical monitor of the study is informed, so that he or she, in turn, informs the Scientific Committee and the Pharmacovigilance Department of the sponsor, and subsequently informs the Research Ethics Committee. Regarding non-serious adverse events, these will be recorded and appropriately addressed, and the corresponding regulatory entity will be informed about the safety profile of the investigational product or investigational drug in the final report of the clinical trial.
- G. The recording of the outcome of the adverse event, suspected adverse reaction, or adverse reaction to medication depends substantially on the principal investigator's monitoring of the participant, since the majority of adverse phenomena are expected to be ophthalmic in nature (see the safety profile section in section 5.3 and in the investigator's manual). However, systemic alterations may exist. Therefore, at the investigator's discretion, the participant's withdrawal or retention will be considered, in accordance with the provisions of section 6.2.2 Exclusion criteria of this research protocol.

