6.2.2 Exclusion criteria

6.2.2.1 General criteria

- Subjects with a history of hypersensitivity to any of the components of the investigational products.
- Subjects who are users of topical ophthalmic medications of any pharmacological group.
- Subjects who use medications by any other route of administration.
- Pregnant or breastfeeding women.
- Women with no history of bilateral tubal obstruction , oophorectomy or hysterectomy, who do not ensure a hormonal contraceptive method or intrauterine device during the study period.
- Subjects with participation in clinical research studies 90 days prior to inclusion in this study.
- Known diagnosis of liver disease
- Inability to attend or respond to assessments conducted at each visit.
- Positive smoking (specified as cigarette consumption regardless of quantity and frequency)
- Positive alcoholism (specified as the consumption of alcoholic beverages, regardless of quantity and frequency, during the study intervention period).
- Contact lens wearers.

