6.2.3 Elimination criteria

- Withdrawal of the consent letter under information.
- Presentation of a serious adverse event.
- Non-tolerability or hypersensitivity to any of the compounds used during the tests (fluorescein, lissamine green , tetracaine)
- Non-tolerability or hypersensitivity to any of the investigational drugs.
- Adherence < 50% determined by subject's diary.

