6.3.3 Concomitant treatments and interventions permitted and prohibited during the study

The use of concomitant medications by any route of administration will not be permitted during the intervention period, except for those specified for the study procedures. The objective of this restriction is to avoid drug interactions that could alter the results of the evaluated variables.

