6.5.1 Procedures to be performed per visit

6.5.1.1 Scrutiny visit

- Signature of informed consent: refers to the signing of the written informed consent document. See 10.3 Consent
- General and ophthalmological medical history: refers to the technical, clinical, and legal document that chronologically records the patient's health conditions, medical procedures, and other procedures performed on the patient. It includes a comprehensive ophthalmological history and examination to determine the patient's eligibility, i.e., evaluation of both eyes and ocular adnexa, slit-lamp examination of the ocular surface and anterior segment, and fundoscopy . If the patient is recruited from the study center's established office, the existing medical history may be used; only one update is required.
- Laboratory sampling: see 6.4.3.9 Laboratory tests.
- Pregnancy test: see 6.4.3.8 Pregnancy test.
- Eligibility criteria: Refers to the PI's review, which verifies that the subject can be included in the study if they meet the inclusion criteria and do not meet the exclusion criteria. See 6.2 Eligibility criteria
- Intraocular pressure: see 6.4.3.5 Intraocular pressure
- Visual capacity: see 6.4.3.1 Visual capacity
- TRL: see 6.4.3.7 Tear film break-up time
- Ocular surface stains: see Ocular surface stains
- Vital signs: see 6.4.3.6 Vital signs

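### The protocol gives different or undefined dispositions for a subject with an adverse event, and the only post-baseline Eye Comfort Index depends on which passage is followed

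*Protocol*

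**What the plan says.** **Removal after entry.** Protocol 6.2.3 (Elimination criteria) includes "Presentation of a serious adverse event" and "Non-tolerability or hypersensitivity to any of the investigational drugs". Neither item carries a qualifier or mentions the investigator's judgement.

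**Withdrawal after an event.** Step G of 9.3.1.3, under a heading about serious adverse events, states that "at the investigator's discretion, the participant's withdrawal or retention will be considered, in accordance with the provisions of section 6.2.2 Exclusion criteria".

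**The list that step G cites.** Section 6.2.2 is used at screening, where the investigator "verifies that the subject can be included in the study if they meet the inclusion criteria and do not meet the exclusion criteria" (6.5.1.1). It has no item on an event that arises during the study. Its general criteria do include "Subjects who are users of topical ophthalmic medications of any pharmacological group" and "Subjects who use medications by any other route of administration".

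**Medication during the study.** Section 6.3.3: "The use of concomitant medications by any route of administration will not be permitted during the intervention period". The only exception is for drugs used in the study procedures.

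**Treatment of events.** Section 9.3.1 makes pharmacological management part of the investigator's duties, and step C of 9.3.1.3 has the investigator decide the treatment. Section 9.3.1.1 instructs: "Include among concomitant medications the therapy used for the pharmacological management of the adverse" event.

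The SAP has no rule on withdrawal after an event.

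**The concern.** Three passages bear on whether a subject with an event continues, and they do not give one answer. For a serious event, one list names it as a ground for elimination while another passage leaves the decision to judgement. The passage that gives the discretion refers the investigator to a list written for entry. A drug given for an event falls under a ban with no exemption, yet the same protocol foresees such treatment.

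What is at stake is outcome data. After baseline, the Eye Comfort Index is completed only at the Final Visit, and the only post-treatment laboratory sample is taken then (6.4.4 and 6.5). No early-withdrawal visit is scheduled. For a missed appointment that cannot be rebooked, 8.1.1 asks as a minimum only about adverse events and the reason for stopping. Section 8.3.3, despite its title, gives no method for missing data. A subject who leaves before Day 11 therefore has no post-baseline value for the primary tolerability outcome.

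**Working it through.** The point rests on comparing text; no figure in the plan has to be reproduced.

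**Step 1: each type of subject against each passage.** Step G sits under a serious-event heading, but step F of the same section also deals with non-serious events. The last three rows assume that step G covers them too.

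| Subject | 6.2.3 | Step G with 6.2.2 | 6.3.3 |
|---|---|---|---|
| Serious event | Listed, no discretion stated | Withdraw or retain, at discretion | Depends on treatment |
| Non-serious, study drug not tolerated | Listed, no discretion stated | Withdraw or retain, at discretion | Depends on treatment |
| Non-serious, tolerated, treated with a drug during the intervention period | Not listed | Discretion; the entry list names medication users, if it is applied after entry | Ban applies; no exemption and no consequence stated |
| Non-serious, tolerated, untreated | Not listed | Discretion; no matching item in the entry list | No breach |

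The first two rows conflict: a listed ground for elimination stands against a choice. In the third row the disposition is undefined, because it depends on which list is used and on what a breach of 6.3.3 entails. In the fourth row nothing conflicts.

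**Step 2: which data are exposed.**

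- Adverse events: 8.3.1 reports all eyes of randomised participants, and the SAP (Methods of Analysis) reports all randomised eyes after instillation. Elimination does not by itself drop the event.
- Pressure, visual capacity, break-up time, staining and vital signs: also measured at Visit 1 (Day 5 ± 2), so a later withdrawal loses only the final value.
- Eye Comfort Index and laboratory tests: no post-baseline value before the Final Visit, so both are lost entirely.

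**Step 3: direction.** Section 8.3.1 and the SAP call the product safe and tolerable when there are no clinical or statistical differences in all primary variables. If subjects who tolerate a product badly are the ones without a final index, the arm with worse tolerability loses more of its high scores and the observed difference shrinks. Fewer observations also make a significant difference harder to reach. Both effects favour the no-difference conclusion.

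**Step 4: scale.** One subject is 1/16 = 6.25% of an arm. The documents give no rate of serious or drug-treated events, so the rates below are assumptions. The chance of at least one such subject among 32 is 1 − (1 − p)^32:

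| Assumed p | Expected number, 32p | Chance of at least one |
|---|---|---|
| 2% | 0.6 | 48% |
| 5% | 1.6 | 81% |
| 10% | 3.2 | 97% |

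**The case against.** The strongest defence is that step G contains a slip. It probably meant the neighbouring section 6.2.3; the same step sends the reader to 5.3 for a safety profile, and 5.3 is the Problem Statement. On that view the medication items in 6.2.2 describe candidates for entry and were never meant for a randomised subject treated for an event. This is plausible, and it would remove the route from treatment to exclusion. It would not remove the discretion in step G against the unqualified items in 6.2.3, nor supply the missing statement on event therapy in 6.3.3.

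Second, 9.3.1.1 says what to record, and recording a therapy does not authorise it. That is fair, so 6.3.3 against 9.3.1.1 alone is a gap. But 9.3.1 and step C go further than recording, and the ban still has no exemption.

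Third, safety information is safeguarded. All randomised eyes are reported, events are followed to resolution (9.3.1.2, with a 30-day limit for chronic ones), and 8.3.3 keeps data from anyone who completed Visit 1. This stands, and it limits the point to the comfort index, laboratory tests and later secondary measures.

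A reader might infer more than the documents support:

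- *The same subject is both retained and removed.* Step G permits either outcome and requires neither.
- *A treated subject must be removed.* Section 6.3.3 states no consequence, and 6.2.3 does not list use of a prohibited drug.
- *Every treated event breaches the ban.* The ban covers the intervention period, and treatment lasts 10 days. An event first treated after that is outside it.

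The adverse event care diagram (Figure 4) is not reproduced in the available text and could not be checked.

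**Conclusion.** The inconsistency is real but limited. For a serious event or non-tolerability, 6.2.3 and step G of 9.3.1.3 give different dispositions. For a tolerated event treated with a drug during the intervention period, the disposition is undefined. The reference to 6.2.2 points to a list with no rule for the situation.

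The documents do not support a conclusion that the primary safety outcome is lost. The exposure is the only post-baseline Eye Comfort Index, the final laboratory sample and the later secondary measures, at 6.25% of an arm per subject. How many subjects would be affected cannot be derived from the plan. The stated direction of bias assumes that withdrawal is more common among subjects who tolerate the product badly, which is what the 6.2.3 criteria imply. With 16 per arm and a success rule based on finding no difference, the passages should be reconciled.

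**What to change.** 1. Reconcile 6.2.2, 6.2.3, 6.3.3, 9.3.1.1 and step G of 9.3.1.3 so that one stated rule governs withdrawal after randomisation. Say for each ground whether it is mandatory or discretionary, and make the status of drug treatment for an event consistent throughout. The content of the clinical rule is for the sponsor.
2. Whichever rule is chosen, perform the already planned Final Visit assessments (comfort index, ocular examination, vital signs, laboratory sample) on the day of withdrawal where the subject agrees, and record the treatment day.
3. State in the SAP how these early values enter the analysis.

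**Cost.** The first item needs a corrected cross-reference and a few sentences. The second adds no new type of assessment, but it means an occasional unscheduled visit and changes the activity schedule, which goes through the amendment route in 10.2. There is one measurement drawback. The comfort index asks about the past week and application starts on Day 1, so a score taken before about Day 7 partly covers pre-treatment days. Such scores should be flagged in the analysis. They remain more informative than no post-baseline score.
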